6.2.2 Confirmatory Secondary Endpoints

The confirmatory secondary efficacy endpoints in this study are the following:

- SE1=Improvement from Baseline at three months in Quality of Life in Essential Tremor (QUEST). SE1 will be calculated as follows:
 - Categorize the 30 questions into 5 dimensions as follows:
 - Communication: #1 – #3
 - Work and Finances: #4 – #9
 - Hobbies and Leisure: #10 – #12
 - Physical: #13 – #21
 - Psychosocial: #22 – #30
 - Score all applicable questionnaire answers as follows:
 - Never = 0
 - Rarely = 1
 - Sometimes = 2
 - Frequently = 3
 - Always = 4

Note:

- ✓ All questions answered “N/A” will be excluded from the calculation (only questions 4, 5, 7, 8 and 14 can be answered “N/A”)

- ✓ Questions 6, 7, 11 and 12 can only be scored at two values – either a 0 or a 4
- For each subject, calculate dimension score as a percentage of total possible score for each dimension separately. Denote dimension score for dimension [i] at visit [k] as $DS_{[i,k]}$, then:

$$DS_{[i,k]} = \frac{\text{Total applicable points}_{[i,k]}}{\text{Total possible points} (\# \text{ of applicable questions} \times 4)_{[i,k]}} \times 100$$

Note: missing data should be imputed as described in Section 7.2.1.

- For each subject, calculate QUEST summary of dimensions total score as a mean of the five dimension scores. Denote QUEST summary of dimensions total score at visit [k] as $QUEST_{[k]}$, then:

$$QUEST_{[k]} = \frac{\sum_{i=1}^5 DS_{[i,k]}}{5}$$

Note: lower QUEST_[k] scores are better than higher scores.

- For each subject, calculate SE1 as follows:

$$SE1 = \frac{QUEST_{[\text{Baseline}]} - QUEST_{[3 \text{ months FU}]}}{QUEST_{[\text{Baseline}]}}$$

Note: higher SE1 values represent improvement.

- SE2=Percent Improvement from Baseline at twelve months post-treatment in the treated (contralateral) upper extremity CRST sub score. SE2 will be calculated similarly to PE from the previous section, based on 12 months FU data.
- SE3=Percent Improvement from Baseline at three months post-treatment in functional disabilities CRST total score, as measured by CRST Part C. Note, that Part C is performed by Site Assessor only. SE3 will be calculated for each subject as follows:
 - Denote functional disabilities CRST Part C total score at visit [k] as $CRST_C_{[k]}$, then:

CRST_C_[k] = average of answers to items #16-#23 at visit [k]

Note: if no more than two items are missing, the average will be calculated over the available items; otherwise, CRST Part C total score will be considered missing and should be imputed as described in Section 7.2.3.

- Calculate SE3 as follows:

$$SE3 = \frac{CRST_C_{[Baseline]} - CRST_C_{[3 \text{ months FU}]}}{CRST_C_{[Baseline]}} \times 100$$

Note: higher SE3 values represent improvement.

6.2.3 Additional Secondary Endpoints

The additional secondary endpoints in this trial include, for each subject:

- Clinical Rating Scale for Tremor (CRST) Parameters:
 - Part A and B CRST Score, as assessed by Core LAB Reviewer:
 - For treated side of the body = CRST_[contralateral, k], as defined in Section 6.2.1
 - For non-treated side of the body = CRST_[ipsilateral, k], which is defined similar to CRST_[contralateral, k] when using values obtained from upper extremity ipsilateral to the side of brain being treated
 - Part B Score for treated side of the body, as assessed by Core LAB Reviewer, for each motor task
 - Part C Score, as assessed by Site Assessor:
 - For each item separately
 - Overall, defined as a sum of all individual items
 - Overall CRST Score, defined as “Total A + Total B + Total C”, where:

Total A = sum of all severity scores of Part A items (1-10 at rest, posture and action/intention), as assessed by Core Lab Reviewer, excluding Head Tremor at Rest

Total B = sum of all severity scores of Part B items (11-15, right and left), as assessed by Core Lab Reviewer

Total C = sum of all severity scores of Part C items (16-23), as assessed by Site Assessor

- Quality of Life in Essential Tremor Parameters, as assessed by QUEST questionnaire:
 - Overall Quality of Life Score, as defined by CRF field “Overall, how would you rate your quality of life?”
 - Waking Hours with Tremor in Any Body Part, as defined by CRF field “On a typical day, how many of your waking hours do you have tremor in ANY body part?”
 - Tremor Severity Score, separately for the following categories:
 - Head
 - Voice
 - Treated arm/hand
 - Non-treated arm/hand
 - Treated leg/foot
 - Non-treated leg/foot
 - QUEST Parameters (based on questions 1-30), as defined in Section 6.2.2:
 - Dimension Score ($DS_{[i, k]}$), separately for each dimension
 - Summary of Dimensions Total Score ($QUEST_{[k]}$)

7 Handling of Missing Data

ITT analysis population: missing confirmatory primary and secondary efficacy data will be imputed using the last observation carried forward (LOCF) method, as described in Sections 7.1 and 7.2 below. Other missing data will not be imputed; only observed data will be used.

Safety, PP and Crossover analysis populations: all missing data will not be imputed; only observed data will be used.

7.1 Imputation of Confirmatory Primary Efficacy Data

Confirmatory primary efficacy endpoint (PE) is considered missing if either Part A or Part B at 3 Months FU is missing.

Imputation of Part A

Part A is considered missing if at least two out of the three individual rates within item #5 (or #6) are missing. Missing rates at 3 Months FU will be imputed using LOCF method, i.e. rates from 1 Month FU will be carried forward. If a single individual rate is obtained and two other rates are missing, the non-missing rate will be taken as is and will not be imputed.

Imputation of Part B

Part B is considered missing if more than one required items is missing. Missing items at 3 Months FU will be imputed using LOCF method, i.e. items from 1 Month FU will be carried forward. The obtained items will be taken as is and will not be imputed.

7.2 Imputation of Confirmatory Secondary Efficacy Data

7.2.1 Imputation of Confirmatory Secondary Endpoint 1 (SE1)

SE1 is defined as average over five QUEST dimension scores. Thus, SE1 is considered missing if at least one dimension score is missing. Below we define when and how each of these dimension scores should be imputed.

Communication, Work and Finances, Hobbies and Leisure Dimensions

The dimension score is considered missing if at least one of applicable items (within a specific dimension) is missing. Missing applicable items will be imputed using LOCF method.

Physical and Psychosocial Dimensions

The dimension score is considered missing if more than two applicable items (within a specific dimension) are missing. Missing applicable items will be imputed using LOCF method.

7.2.2 Imputation of Confirmatory Secondary Endpoint 2 (SE2)

The imputation of SE2 will be done similarly to PE, as described in Section 7.1.

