5.7 Missing Data

Analyses will be performed on both observed and data with missing values imputed per the method of last observation carried forward (LOCF) where data for missing visits is assigned the value of the previous visit. Analyses will include the presentation of results calculated based on the intent-to-treat principle. A sensitivity analysis of the baseline characteristics of subject drop-outs or withdrawals will also be performed to evaluate the presence of a drop-out bias.

5.8 Statistical Analysis Plan.

A comprehensive statistical analysis plan, including sensitivity analyses for example, will be completed in consultation with FDA prior to performing any data review or analysis for all data collected through Month 12.

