15.6 Missing Data

Analyses will be performed on both observed and data with missing values imputed per the method of last observation carried forward (LOCF) where data for missing visits is assigned the value of the previous visit.

NOTE:

All Demographic, Screening, Baseline, Treatment and some amount of Follow-up data are collected under ET002 or ET002-CA and these data will be used in coordination with that collected under this protocol.

15.7 Statistical Analysis Plan.

The analysis will be performed based upon the Statistical Analysis Plan (“SAP”) procedures as defined for the pivotal study (FDA Approval of SAP under IDE

Supplement G120246/S06). Please note, however, that for the PAS, all analyses will be performed using the site assessor data only.

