18 POTENTIAL BENEFITS

The pivotal trial cohort of subjects being followed in this study demonstrated a powerful, robust result at Month 3 with the ExAblate group experiencing a highly significant improvement in the PE and all secondary confirmatory endpoints (See table). The outcomes were essentially unchanged and still favorable by Month 12.

| Efficacy Analysis Summary | | | | | |
|---|--------------------------------------|------------------|------------------------------|---------------------------------------|---------------------------|
| | % of Improvement At Month-3 – ITT | | | % of Improvement At Month 12 – ITT | |
| | ExAblate (N=56) | Sham (N=20) | Between Groups p-value | ExAblate (N=56) | P-value Vs Baseline |
| Primary Endpoint – Composite Tremor/Motor Function | 46.9% | - 0.1% | p< 0.001 | 39.6% | p< 0.001 |
| ..Lower 95% CI | 40.3% | -9.6% | | 34.0% | |
| Upper 95% CI | 53.5% | 9.5% | | 45.3% | |
| CRST, Part A- Tremor “Posture” | 64.3% | - 4.4% (n=17) | P<0.001 | 65.5 % | p< 0.001 |
| ..Lower 95% CI | 52.1% | -26.9 | | 54.7 % | |
| Upper 95% CI | 76.5% | 18.2 | | 76.3 % | |
| CRST, Part C | 63.8% | 1.8% | p< 0.001 | 64.0% | p< 0.001 |
| ..Lower 95% CI | 55.3% | -6.7% | | 55.2% | |
| Upper 95% CI | 72.4% | 11.1% | | 72.7% | |
| QUEST | 43.2% | 5.0% (n=19) | p< 0.001 | 47.1% | p< 0.001 |
| ..Lower 95% CI | 34.3% | -14.9% | | 36.5% | |
| Upper 95% CI | 56.3% | 36.2% | | 62.1% | |

A negative sign “-“ indicates worsening

The safety profile for the pivotal trial cohort demonstrated a rather benign and favorable profile in relation to benefit. Many events were considered Transient and Unrelated and most resolved. The remaining events were Procedure or Thalamotomy related events. All but one were Mild / Moderate in severity. Only 1 serious, related event occurred of Moderate Numbness/Tingling of the thumb which interfered with the subject's ability to hold a pen and write at work.

This PAS is simply an observational study to collect longer-term safety and durability of treatment effect in the IDE study population all the way out to 5 years.

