10.6.6 Sensitivity Analyses

The method for imputation of missing data for the confirmatory primary efficacy analysis is defined as Last Observation Carried Forward (LOCF). In the case that there is a large amount of missing data, additional methods of imputing missing data will be used to examine the robustness of the treatment effect.

All sensitivity analyses will be conducted on the ITT analysis population and will repeat the confirmatory primary efficacy analysis.

Worst Case

Worst Case analysis will be assessed by imputing missing values as follows:

- The 10th percentile PE value of ExAblate group will be imputed to subjects with missing data in ExAblate group
- The 90th percentile PE value of Sham group will be imputed to subjects with missing data in Sham group

Descriptive statistics with comparison p-value will be provided (**Error! Reference source not found.**).

Best Case

Best Case analysis will be assessed by imputing missing values as follows:

- The 90th percentile PE value of ExAblate group will be imputed to subjects with missing data in ExAblate group
- The 10th percentile PE value of Sham group will be imputed to subjects with missing data in Sham group

Descriptive statistics with comparison p-value will be provided (**Error! Reference source not found.**).

Multiple Imputations

Multiple Imputations analysis will be assessed by creating 10 imputed data sets using the multiple imputation procedure (PROC MI in SAS®). Various baseline characteristics will be considered for the purpose of imputation. Missing PE values will be imputed. The confirmatory primary efficacy analysis will be repeated on each of 10 imputed data sets (**Error! Reference source not found.**). The summarized result (using PROC MIANALYZE in SAS®) will be presented (**Error! Reference source not found.**).

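### Carrying the last score forward builds persistence into the Month 12 (SE2) and Year 2-5 estimates; the planned missing-data checks cover only Month 3

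*SAP*

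**What the plan says.** SAP Section 7 sets the rule for the ITT population: "missing confirmatory primary and secondary efficacy data will be imputed using the last observation carried forward (LOCF) method". Section 7.2.2 applies it to SE2: "The imputation of SE2 will be done similarly to PE, as described in Section 7.1". The section it points to, 7.1, is written for Month 3 and names a single source visit: "rates from 1 Month FU will be carried forward". No source visit is named for Month 12, although the Core Lab also scores Months 3 and 6.

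For missed Year 2-5 visits, ET002-LTF Section 15.6 prescribes LOCF, "where data for missing visits is assigned the value of the previous visit", beside an analysis of observed data. Section 5.7 of the main protocol has the same pair: "Analyses will be performed on both observed and data with missing values imputed", again by LOCF.

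SAP Section 10.6.6 lists worst-case, best-case and multiple-imputation analyses, to be run if the amount of missing data is large (no threshold is given). Their scope is fixed: "All sensitivity analyses will be conducted on the ITT analysis population and will repeat the confirmatory primary efficacy analysis". That is the Month 3 endpoint.

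Under SAP Section 10.6.3, SE2 is tested in the ExAblate arm alone, with the mean compared with zero.

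**The concern.** SE2 and the long-term study ask whether the benefit lasts. For a subject who misses the visit or is lost to follow-up, LOCF answers that question by assumption: the last benefit seen is taken to be still there. If benefit wanes, the estimated durable effect is too high, by more as more subjects are missing and as the gap since their last visit grows.

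The sponsor's own material makes waning plausible. ET002-LTF Section 18 reports a lower composite at Month 12 than at Month 3, and Section 16 anticipates that some patients will not sustain their improvement. That section also lists sustained tremor/motor benefit at five years as a specific question for the approval. What is at stake is the size of the Month 12 and Year 2-5 benefit. Because SE2 is compared only with zero, almost any retained benefit passes, and the estimate and its interval carry the information.

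**Working it through.** **Inputs.** ET002-LTF Section 18, ExAblate arm, ITT, N = 56: composite 46.9% at Month 3 (95% CI 40.3 to 53.5) and 39.6% at Month 12 (34.0 to 45.3), the latter with p < 0.001 against baseline. The number actually observed at Month 12 is not given. I assume 3, 6 or 11 of 56 missing (5%, 11%, 20%); the upper end matches the 20% dropout allowance in main protocol Section 5.4.

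**1. Reproduce the reported Month 12 result.** CI half-width = (45.3 − 34.0)/2 = 5.65. SE = 5.65/2.004 = 2.82 (t quantile, 55 df). SD = 2.82 × √56 = 21.1. t = 39.6/2.82 = 14.0, which agrees with p < 0.001.

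**2. Did benefit wane?** Mean improvement in the ExAblate arm, same table:

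| Measure | Month 3 | Month 12 | Change |
|---|---|---|---|
| Composite (the SE2 measure) | 46.9 | 39.6 | −7.3 |
| Part A posture | 64.3 | 65.5 | +1.2 |
| Part C | 63.8 | 64.0 | +0.2 |
| QUEST | 43.2 | 47.1 | +3.9 |

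Only the composite declined.

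**3. Excess if Month 3 is carried to Month 12.** Per imputed subject, on average: 46.9 − 39.6 = 7.3 points. On the mean: 7.3 × 0.10 = 0.73 and 7.3 × 0.20 = 1.46. If the reported 39.6 already contains carried values, the observed decline is larger: with 11 carried at 46.9, the other 45 average (56 × 39.6 − 11 × 46.9)/45 = 37.8.

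**4. Comparison with loss of benefit.** Suppose 39.6 includes k values carried at 46.9. Replace those k by the 10th percentile (the worst-case rule of 10.6.6, normal approximation: observed mean − 1.2816 × 21.1) or by 0 (return to baseline), and repeat the one-sample t-test.

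| k of 56 | Mean of observed | Month 12 mean, 10th percentile | Month 12 mean, return to baseline | Fall from 39.6 at return to baseline | t at return to baseline |
|---|---|---|---|---|---|
| 3 (5%) | 39.2 | 37.7 | 37.1 | 2.5 | 12.4 |
| 6 (11%) | 38.7 | 35.8 | 34.6 | 5.0 | 11.1 |
| 11 (20%) | 37.8 | 32.5 | 30.4 | 9.2 | 9.4 |

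The fall is k/56 × 46.9; for k = 11, 11/56 × 46.9 = 9.2.

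**5. The SE2 test.** Every case stays at p < 0.001. With 11 missing, each imputed value would have to be about −84% (a marked worsening) before significance was lost.

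**6. Years 2-5.** The documents give neither attrition nor a rate of decline. If, say, 10% are last seen at each of Month 12 and Years 2, 3 and 4, and benefit falls by d points a year, the Year 5 excess is 0.10 × d × (4 + 3 + 2 + 1) = d. The result simply returns the assumed decline, so I give no Year 5 figure.

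**The case against.** The case against is substantial, and much of it stands.

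- **The SE2 decision is safe.** A reader might infer that SE2 success depends on the imputation. Steps 4 and 5 show that it does not.
- **The bias is not universal.** A reader might infer that LOCF always favours durability. On posture, Part C and QUEST, carrying the Month 3 mean forward would be neutral or slightly conservative, and for those rows the statement "The outcomes were essentially unchanged and still favorable by Month 12" is fair. For the composite, the Month 3 and Month 12 intervals overlap. They come from the same arm, so overlap is not a test of change, and no paired comparison is reported.
- **Non-imputed analyses are planned.** SAP 10.6.4 repeats SE2 in the per-protocol population, where Section 7 allows no imputation. It also summarises the contralateral score over time in ITT and per-protocol subjects; as an additional endpoint, that score is not imputed. Main protocol 5.7 and ET002-LTF 15.6 also call for observed-data results. These avoid crediting a missing subject with persistence, but they drop that subject, so none allows for lost benefit.
- **Counts by visit are already planned for the pivotal study.** SAP Sections 10 and 10.1 provide subject numbers, accountability by visit and last available visit. ET002-LTF 14.3 asks sites to recover at least a tremor assessment after a missed visit.
- **Month 6 may be the source visit.** Main protocol 5.7 takes the previous visit, which is Month 6 for a subject who misses only Month 12. The 7.3 points then do not apply. The excess would be smaller if the decline was gradual, but no Month 6 mean is given.
- **A mixed model is not a complete answer.** It assumes missing at random. Changing the confirmatory SE2 analysis once Month 12 results are known would also be post hoc. Both points shape the fix.

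**Conclusion.** The concern holds for the size of the durable effect, and as an inexpensive improvement rather than a threat to the trial's conclusions. LOCF assumes persistence in exactly the estimates meant to measure it, the SE2 composite did decline, and no planned analysis of Month 12 or Years 2-5 lets a missing subject have lost benefit.

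If Month 3 is the visit carried, the Month 12 mean is overstated by about 0.7 to 1.5 points at an assumed 10% to 20% missing, small beside the CI half-width of 5.65. Measured against full return to baseline, an extreme assumption, the gap is about 2.5 to 9.2 points at an assumed 5% to 20% missing. Both ranges rest on missing counts that the documents do not report and on imputed subjects having had average Month 3 benefit. The documents support neither a changed SE2 test result nor a numerical Year 5 bias.

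**What to change.** 1. **Main durability estimate.** Report the Month 12 mean with 95% CI from a repeated-measures mixed model in the ExAblate arm, using all observed Core Lab scores (Baseline and Months 1, 3, 6 and 12) and expressed as percent improvement. Do the same for Years 2-5 on site scores, the only scores that ET002-LTF 15.7 uses. Keep LOCF as a sensitivity analysis.
2. **Sensitivity analyses.** Extend SAP 10.6.6 to SE2 and to Years 2-5, and drop the undefined condition on the amount of missing data. Include a worst-case or return-to-baseline analysis, because the mixed model assumes missing at random.
3. **Carried visit.** State in SAP 7.2.2 which visit is carried to Month 12.
4. **Status.** Where results are already known, label the added SE2 analyses as supplementary and leave the confirmatory test as it is.

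The cost is SAP and ET002-LTF wording and one standard model on scores already scheduled, with no new data collection. The downside is slightly wider intervals and a possibly lower durability figure.

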7.2.3 Imputation of Confirmatory Secondary Endpoint 3 (SE3)

CRST Part C total score is considered missing if more than two items are missing. Missing items at 3 Months FU will be imputed using LOCF method (where applicable). The obtained (non-missing) items will be taken as is and will not be imputed.

8 Data Derivation and Transformation

Data not originally part of the CRF will be derived as follows:

- Age [years] = (Date of Informed Consent – Date of Birth + 1) / 365.25
- BMI [kg/m²] = Weight (kg) / Height (m)²
- Time from Initial ET Symptoms [years] = (Date of Informed Consent – Approximate Date of Initial ET Symptoms¹ + 1) / 365.25
- Time from Initial ET Diagnosis [years] = (Date of Informed Consent – Date of Initial ET Diagnosis¹ + 1) / 365.25
- Time from First ET Medical Therapy [years] = (Date of Informed Consent – Date of First ET Medical Therapy¹ + 1) / 365.25
- Handedness (Right / Left) is indicated by CRF field “Right or Left Handed” on Baseline CRST Form, as assessed by Site Assessor
- Treated Side of the Body (Right / Left) is defined as the opposite side of the brain being treated, indicated by CRF field “Side of Brain being treated” on the ExAblate Treatment Form
- Time Inside Scanner [min] = Time Out of Scanner – Time In Scanner
- Sonication Treatment Time [min] = Sonication End Time – Sonication Start Time
- Target Size [cm³] = $\frac{4}{3}\pi(\frac{1}{2} \times SI[cm] \times RL[cm] \times AP[cm])$, where SI, RL and AP are the target dimensions Superoinferior, Right-Left and Anteroposterior respectively, as collected on the ExAblate Treatment Form
- The following will be provided by InSightec:

¹ If only Day is missing then the 15th of the Month will be imputed; if both Day and Month are missing then the 1st of July will be imputed.

- By-subject listing of all protocol deviations
- Coding of all Adverse Events

9 Interim Analysis

No interim analysis is planned for the ET-002 study.

10 Statistical Analysis

All statistical analyses will be carried out using SAS® Version 9.2 or higher under Windows® Server 2008 Terminal.

The data will be summarized in tables listing the mean, standard deviation, minimum, median, maximum and number of subjects for continuous data, or in tables listing count and percentage for categorical data where appropriate.

